 - Feasibility Hypothesis: $\geq 75\%$ of patients approached for recruitment will agree to participate

Fidelity proportions will be calculated for adherence and retention at the end of the intervention using the following:

1. Proportion adherent to nutrition intervention will be computed by the number of empty supplement containers divided by the number of possible supplement containers that could be consumed.

2. Proportion adherent to nutrition intervention will also be computed by the number of meals consumed that are 25 grams of protein divided by the number of possible meals that could be achieved. For the PoshControl arm, adherence will be assessed by the number of dietary changes they make based on the educational handout provided to them at baseline. These will be determined by using diet records for 3 days prior to surgery and 3 days following surgery. Diet food records are valid method for collecting dietary intake data and have been administered in Veteran populations.⁴² We have experience administering and analyzing this data.¹

- Adherence Hypothesis: $\geq 75\%$ of the time PeriHab participants will adhere to the intervention and $\geq 75\%$ of the time controls will show at least one recommended dietary change in their 3-day diet record

3. Proportion retention will be computed by dividing the number of retained subjects at the end of the intervention by the total number randomized into the study.

- Retention Hypothesis: $\geq 80\%$ of participants will remain in the study for the duration of the trial

We will calculate these rates of retention and adherence and their respective confidence intervals overall and by group. While non-powerful, we will assess if these rates differ by chi-square test of proportion and Poisson regression respectively. In a series of sensitivity tests, we will assess if adherence overall was impacted by demographic or symptomatic variables (such as chronic health conditions, living arrangements, surgery, functional status, and nutrition status).

Acceptability will be assessed by:

1. Calculating levels of attrition.

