Aim 1.2 Analysis Plan: This design is a two-armed clinical trial, with replicate measures at three time points: baseline, two, and six weeks. Since subjects are randomized to either PeriHab or PoshControl arm, and the groups are presumed equal at baseline, the analysis is straightforward. Following the Good Clinical Practice Guidelines for the analysis of a clinical trial, we will employ mixed models,⁴³ analyze under an Intent to Treat (ITT) criteria, and control for baseline and assess the impact of Time, Treatment Group and the interaction of these variables on the outcomes. Relative to the usual repeated measures designs, mixed models have several advantages: 1) missing values present no particular difficulties in estimation and the estimates are unbiased as long as the set of variables leading to MAR are estimated, 2) the usual assumption of conditional independence (compound symmetry) used in standard repeated measures need not be made, and 3) the actual times of measurement need not be equivalent across subjects. Controlling for the individual baseline values for the particular outcomes, the trajectories over time and differences in those trajectories will be assessed. Following the statistical principles section from the International Conference on Harmonization, we will select covariates (e.g., age, race, number of comorbidities) for the primary models a priori, but we also will conduct auxiliary sensitivity analyses that evaluate whether potential group imbalances bias the treatment effect estimate. These analyses will be performed using conventional testing for confounding.

For any particular outcome, the general form of the model will be:

$$Y_{it} = \beta_0 + \beta_1(\text{group}) + \beta_2(\text{time}_t) + \beta_3(\text{group} * \text{time}_t) + \beta_4(\text{covariates}) + \varepsilon_{it}$$

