Secondary Outcomes: At the conclusion of the study, we will have a rich database with which to conduct follow-up exploratory analyses. We will perform multiple exploratory analyses of the remaining measures. In addition to the impact of the intervention on the secondary outcomes, we will assess mediation of the group effect on the primary outcome by demographic, comorbid and adherence variables. Subjects may differ in their process of change depending on baseline demographic and functional status values. Second, we will assess the functional form of the change over time, by looking at non-linear functions of change. For example, change in function and performance is likely to be non-linear, initially changing quickly and leveling off at points distal from baseline. It would be important to note if this change differed by group. Finally, we will assess whether the trajectories of change, irrespective of group assignment, are similar for individuals. In this application, we have listed several variables, which we expect to change as a result of the intervention. We further hypothesize that all these variables will change in the same pattern. To test this hypothesis, across the

range of outcome measures, we can look at overall change through the use of multivariate tests (Bock⁴⁴ or Anderson⁴⁵) for the singly measured functional items, and by assessment of correlated trajectories for those outcomes measured repeatedly. With appropriate weighting for number of observations per individuals, the correlation between individual trajectories can be assessed. A positive correlation between the trajectories for any two outcomes will indicate that the subjects changed similarly for the 2 outcomes, and will provide additional support for the notion that the intervention had a generalized effect across the outcomes.

Significant correlations would perhaps indicate mechanistic/causal linkage between variables over time, or, from a reliability standpoint, may indicate that the subsequent trial may want to employ summary measures aggregating across outcome measures, or, alternatively, employ multivariate tests across several outcomes to assess the group differences, reducing the chance of Type-I error inherent in the testing of multiple variables.

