The results of these analyses will provide invaluable information regarding the process and functional forms and, potentially, the causal pathways of the intervention process. For example, one important analysis will enter 'level of compliance to the intervention' into the analysis, allowing for a 'per protocol' analysis of the results.

Power Estimate: Estimate effect sizes for the physical function between-group comparisons and the power available to detect effect with two-tailed tests are provided below for the total N= 80. The objective of this pilot study is to perform preliminary evaluation of a nutrition perihabilitation program in malnourished Veterans, in preparation for a larger grant submission. This pilot work will allow us to conduct sample size, effect sizes, and power analyses for a larger clinical trial. To date, no randomized controlled nutrition perihabilitation study has been conducted in malnourished Veterans. As such, we turned to the literature. Gillis et al.,⁴⁶ reported that older adults undergoing colorectal resectioning surgery who were given nutrition supplementation 3 weeks before surgery improved by 23.7 meters on the 6 minute walk test while the arm given nutrition supplement following the surgery declined by -21.3 meters. The pooled standard deviation of these changes was 67.75. Thus, a standard difference of $0.66 = (23.7 - (-21.3))/67.75$ was observed. Differences of this magnitude have been labeled as 'medium' in the statistical power literature (70). Assuming a standard deviation in the change scores of 67.75, n=40 per group, power=80% and alpha=0.05 (two-tailed), we are powered to detect a difference in changes scores of a standardized magnitude of 0.634, in line with the results of Gillis et al.⁴⁶

References

2. Morley J. Decreased food intake with aging. *J Gerontol Med Sci* 2001;56:81-88.

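### Entering compliance into the model and calling the result per-protocol can bias the group effect: compliance arises after randomisation and is scored differently in the two arms

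*Combined protocol and SAP*

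**What the plan says.** The main comparison, in the Aim 1.2 Analysis Plan, is a mixed model in which the sponsor will "analyze under an Intent to Treat (ITT) criteria".

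The Secondary Outcomes text that follows is exploratory: "we will have a rich database with which to conduct follow-up exploratory analyses". It includes a mediation analysis: "we will assess mediation of the group effect on the primary outcome by demographic, comorbid and adherence variables". Its closing paragraph says the results may inform "potentially, the causal pathways of the intervention process", and gives as its example that "one important analysis will enter 'level of compliance to the intervention' into the analysis", "allowing for a 'per protocol' analysis of the results". The plan defines no per-protocol set, no compliance threshold, no compliance variable, no model equation for this step and no causal method.

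Adherence itself is defined in the Aim 2.1 Analysis Plan, under fidelity. One measure is "the number of empty supplement containers divided by the number of possible supplement containers that could be consumed". A second is the share of meals reaching 25 g of protein. The text then gives the control arm its own measure: "For the PoshControl arm, adherence will be assessed by the number of dietary changes they make based on the educational handout". The success criteria differ too: adhering at least 75% of the time in PeriHab, against showing at least one recommended change in the three-day diet record in PoshControl.

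**The concern.** Two features combine.

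First, compliance is a post-randomisation variable. In malnourished surgical patients aged 60 or over, it is plausible that whatever limits eating and drinking supplements also limits physical performance after surgery. If so, a model that conditions on compliance no longer compares the groups that randomisation made comparable.

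Second, the compliance number means different things in the two arms. A coefficient that holds compliance equal across arms then compares, for example, a PeriHab participant at 0.75 of containers with a control participant at 0.75 of a dietary change. No clinical question corresponds to that contrast.

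The per-protocol label and the reference to causal pathways invite readers to take the coefficient as the effect of actually taking the supplement. The pilot's stated purpose is to supply effect sizes for a larger trial, so a distorted estimate could enter that trial's sample size.

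**Working it through.** **The plan's own figure.** The Power Estimate gives a detectable standardised difference of 0.634 with 40 per group, 80% power and two-sided alpha 0.05. A two-sample noncentral t calculation with 78 df gives 0.6343, which agrees. The normal approximation, (1.960 + 0.842) × √(2/40), gives 0.626. This figure is sound, and is used below only as a yardstick.

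**Why the covariate matters.** With equal arms, least squares of outcome Y on group and compliance C gives

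group coefficient = (difference in mean Y) − g × (m_P − m_C)

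where m_P and m_C are mean compliance in PeriHab and PoshControl, and g is the pooled within-arm slope, (cov_P + cov_C)/(var_P + var_C). With no true effect, its expectation is about g × (m_C − m_P). This is zero if g = 0 (compliance unrelated to prognosis) or if the means are equal, as they are after centring within arm. Otherwise it is not zero, and its sign follows the sign of the mean difference.

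**Assumed inputs** (none are in the documents): Y has SD 1 and correlates ρ = 0.3 to 0.5 with an unmeasured severity factor, 42 per arm, one time point, no true effect.

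*Case A, both arms on a 0–1 proportion.* PeriHab mean 0.70, shifting 0.20 per SD of severity. Control mean 0.90, shifting 0.08. Independent compliance noise has SD s. Then

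bias = ρ × (0.20 + 0.08) × 0.20 / (0.20² + 0.08² + 2s²)

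*Case B, proportion against count.* PeriHab mean 0.75, SD 0.20. Control count mean 2, SD 1. Compliance correlates r = 0.3 to 0.5 with severity. Then

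bias = 1.25 × ρ × r × (0.20 + 1)/(0.04 + 1) = 1.442 × ρ × r

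Simulated results use 4,000 null trials per setting, with compliance truncated to 0–1 in case A:

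| Setting | Bias by formula (SD) | Bias simulated (SD) | Rejected at 5% |
|---|---|---|---|
| A, s = 0.10 | 0.25 to 0.42 | 0.27 to 0.45 | 18% to 46% |
| A, s = 0.20 | 0.13 to 0.22 | 0.14 to 0.23 | 9% to 17% |
| B | 0.13 to 0.36 | 0.13 to 0.36 | 7% to 23% |
| A, s = 0 (severity alone sets compliance) | 0.36 to 0.60 | 0.39 to 0.64 | 31% to 75% |

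Truncation explains the small excess over the formula in case A. In null simulations the coefficient averaged about zero when compliance was unrelated to severity, when both arms had the same mean and SD, and when compliance was centred within arm.

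**Effect on sizing the next trial.** With a true difference of 0.634, 40 per arm and ρ = 0.5, the adjusted estimate averaged 0.82 to 0.85 at r = 0.3 and 0.94 to 0.99 at r = 0.5. The inputs were case B and a proportion case with means 0.60 and 0.85 and SD 0.20. Sample size scales with 1/d². A trial sized on 0.82 would have (0.634/0.82)² = 60% of the participants it needs. Sized on 0.99, it would have (0.634/0.99)² = 41%.

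**Would the container measure solve it?** Control is given one supplement a day before surgery: 1 × 14 = 14 containers. PeriHab is given three a day before and after surgery. That is 3 × 42 = 126 under Study Arms and the PeriHab protocol (four weeks after surgery), or 3 × 28 = 84 under Specific Aim 1.2 (two weeks after). A shared ratio would still describe very different burdens. Those sections must be reconciled, because the duration sets the denominator.

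**The case against.** The best defence is that the plan has already contained this analysis. The main analysis is intention-to-treat, the compliance step sits among exploratory analyses, and the causal language is hedged. That stands: a reader might infer that the primary result is compromised, and the documents do not support that.

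It is also fair that the model is inferred. Entering compliance into the analysis is most naturally read as adding a covariate, but no equation or coding is given, and centring within arm would remove the average bias. The container measure is not expressly limited to one arm, and control lids are returned on the day of surgery, so a common pre-operative proportion could be built. The plan does not say that this is the compliance variable, and its only control-specific definition is the count.

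A reader might further infer that the analysis will certainly mislead, or by as much as 0.64 SD with 75% false positives. Neither is supported. The documents give no compliance distributions and no relation between compliance and prognosis. The extreme figures need severity to be the only determinant of compliance, with nothing left for taste, forgetting or motivation.

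Finally, an instrumental-variable estimate is not an obviously better replacement. It requires assignment to act only through protein intake, yet the arms also differ in the number and duration of supplements, sample menus and counselling content.

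**Conclusion.** The point holds as a risk, not a certainty, and it is minor. Followed as written, the plan can produce a biased group coefficient under a per-protocol label, because a post-randomisation variable with no common scale is entered across arms. That is more than missing detail.

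On the assumed inputs, the spurious effect is about 0.13 to 0.45 SD with 7% to 46% false positives, against a detectable difference of 0.634. It disappears if compliance is unrelated to prognosis or is centred within arm. Size and direction depend on quantities the documents do not give, and the illustration uses a single time point rather than the planned two-visit mixed model. The intention-to-treat result and the 0.634 figure are untouched. What is exposed is the exploratory interpretation and any effect size passed to the larger trial.

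**What to change.** In Secondary Outcomes, state that a compliance-adjusted group coefficient will not be reported as a per-protocol or causal effect and will not be used to size the next trial. Report compliance against outcome separately within each arm, on that arm's own measure, as a descriptive association, and name the measure used.

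Optionally, add an exploratory instrumental-variable estimate, with random assignment as the instrument for protein intake in g/kg/day from the weekly 24-hour recalls, which are planned in both arms. State with it that intervals will be wide, that recall is measured with error, and that the exclusion restriction is doubtful for the reasons given above.

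The cost is a few sentences, a little exploratory programming and the loss of a per-protocol headline. No new data collection is needed.
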